6.4.2 Criteria for Conditional Withholding of AMG 673 due to Potential Hepatotoxicity

For subjects who do not meet the criteria for permanent discontinuation of AMG 673 outlined above and have no underlying liver disease, and eligibility criteria requiring normal transaminases and TBL at baseline or subjects with underlying liver disease and baseline abnormal transaminases, the following rules are recommended for withholding of Amgen investigational product:

- Elevation of either AST or ALT according to the following schedule:
 - Any AST or ALT elevation: $> 8 \times \text{ULN}$ at any time
 - Any AST or ALT elevation: $> 5 \times \text{ULN}$ but $< 8 \times \text{ULN}$ for ≥ 2 weeks
 - Any AST or ALT elevation: $> 5 \times \text{ULN}$ but $< 8 \times \text{ULN}$ and unable to adhere to enhanced monitoring schedule
 - Any AST or ALT elevation: $> 3 \times \text{ULN}$ with clinical signs or symptoms which are consistent with hepatitis (such as right upper quadrant pain/tenderness, fever, nausea, vomiting, or jaundice).
- OR: TBL $> 3 \times \text{ULN}$ at any time
- OR: ALP $> 8 \times \text{ULN}$ at any time

AMG 673 should be withheld pending investigation into alternative causes of the laboratory elevations. If the investigational product is withheld, the subject is to be followed according to recommendations in [Appendix A](#) for possible DILI. Rechallenge may be considered if an alternative cause for the elevated liver enzymes (ALT, AST, ALP) and/or elevated TBL (total bilirubin level) is discovered and the laboratory abnormalities resolve to normal or baseline ([Section 2](#)).

Discontinuation of the product should be considered and the decision to re-challenge should be discussed with the Amgen medical monitor before re-initiating treatment with investigational product.

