1	Symptoms are not life threatening and require symptomatic treatment only, eg, fever, nausea, fatigue, headache, myalgias, malaise	
 Administer symptomatic treatment (eg, paracetamol/ acetaminophen for fever, fluids for hypotension). Consider use of tocilizumab 8 mg/kg iv. Up to 3 additional doses can be given 8 hours apart, if needed. Monitor for CRS symptoms including vital signs and pulse oximetry at least Q2 hours for 12 hours or until resolution, whichever is earlier. 	N/A
2	Symptoms require and respond to moderate intervention 
 Oxygen requirement < 40%, OR Hypotension responsive to fluids or low dose of 1 vasopressor, OR Grade 2 organ toxicity or grade 3 transaminitis per CTCAE criteria 	Administer: 
 Symptomatic treatment (eg, paracetamol/ acetaminophen for fever, vasopressors for hypotension) Supplemental oxygen when oxygen saturation is < 90% on room air Intravenous fluids or low dose vasopressor for hypotension when systolic blood pressure is < 100 mmHg. Persistent tachycardia (eg > 120 bpm) may also indicate the need for intervention for hypotension. Consider use of tocilizumab 8 mg/kg IV . Dose may be repeated every 8 hours for up to 3 additional doses. Monitor for CRS symptoms including vital signs and pulse oximetry at least Q2 hours for 12 hours or until resolution to CRS grade ≤ 1, whichever is earlier. For subjects with extensive co-morbidities or poor performance status, manage per grade 3 CRS guidance below.	Institute medical management. If hypotension worsens or persists 2 hours after adequate medical management, interrupt AMG 673 until CRS is Grade ≤ 1. Refer to re-start criteria below. If symptoms progress to grade 3 criteria, see row below. Permanently discontinue AMG 673 if there is no improvement to CRS ≤ grade 1 within 7 days.

Approved

Footnotes defined on next page of the table

Table 5. Grading and Management of Cytokine Release Syndrome

CRS Grade	Description of Severity^a	Minimum Expected Intervention	Instructions for Interruption of AMG 673

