3	Symptoms require and respond to aggressive intervention 
 • Oxygen requirement $\geq 40\%$, OR • Hypotension requiring high dose^b or multiple vasopressors, OR • Grade 3 organ toxicity or grade 4 transaminitis per CTCAE criteria 	Admit to intensive care unit for close clinical and vital sign monitoring per institutional guidelines. Administer dexamethasone (or equivalent) IV at a dose maximum of 3 doses of 8 mg (24 mg/day). The dose should then be reduced step-wise. Administer tocilizumab as an additional therapy in this setting at a dose of 8 mg/kg. Dose may be repeated every 8 hours for up to 3 additional doses.	Immediately interrupt AMG 673 until event resolves to CRS grade ≤ 1 . Permanently discontinue AMG 673 if there is no improvement to CRS \leq grade 2 within 5 days or CRS \leq grade 1 within 7 days. Permanently discontinue AMG 673 if CRS grade 3 occurs at the initial run in dose (ie, at MTD1).
4	Life-threatening symptoms 
 • Requirement for ventilator support OR • Grade 4 organ toxicity (excluding transaminitis) per CTCAE criteria 	Admit to intensive care unit for close clinical and vital sign monitoring per institutional guidelines. Administer dexamethasone (or equivalent) IV at a dose maximum of 3 doses of 8 mg (24 mg/day). Further corticosteroid use should be discussed with the Amgen medical monitor. Additionally, tocilizumab should be administered at a dose of 8 mg/kg. Dose may be repeated every 8 hours for up to 3 additional doses.	Immediately stop the infusion and permanently discontinue AMG 673 therapy.

Approved

Page 2 of 2

CRS, Cytokine Release Syndrome; CTCAE, Common Terminology Criteria for Adverse Events;

IV, Intravenous; MTD = maximum tolerated dose

^a Revised grading system for CRS (Lee et al, 2014)

^b High dose vasopressors (all doses are required for ≥ 3 hours): Norepinephrine monotherapy ≥ 20 $\mu\text{g}/\text{min}$; Dopamine monotherapy ≥ 10 $\mu\text{g}/\text{kg}/\text{min}$, Phenylephrine monotherapy ≥ 200 $\mu\text{g}/\text{min}$, Epinephrine monotherapy ≥ 10 $\mu\text{g}/\text{min}$; If on vasopressin, vasopressin + norepinephrine equivalent of ≥ 10 $\mu\text{g}/\text{min}$; If on combination vasopressors (not vasopressin), norepinephrine equivalent of ≥ 20 $\mu\text{g}/\text{min}$

Re-start of treatment after CRS:

After grade 2 or 3 CRS, the next infusion may be administered if all of the following criteria are met:

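### Protocol 6.4.1-6.4.3 and the CRS rules (Table 5, 6.6, 6.2.1.4) overlap when liver tests rise within CRS, set different re-start and recurrence conditions, and state no precedence

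*Protocol*

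**What the plan says.** **Hepatic rules (Protocol 6.4.1-6.4.3).** Section 6.4.2 introduces its triggers with the words "the following rules are recommended for withholding of Amgen investigational product". They include AST or ALT above 8 x ULN at any time, total bilirubin above 3 x ULN at any time, and AST or ALT above 3 x ULN "with clinical signs or symptoms which are consistent with hepatitis (such as right upper quadrant pain/tenderness, fever, nausea, vomiting, or jaundice". On re-dosing it says: "Rechallenge may be considered if an alternative cause for the elevated liver enzymes (ALT, AST, ALP) and/or elevated TBL (total bilirubin level) is discovered", and it adds that the abnormalities must have returned to normal or baseline. Section 6.4.3 requires permanent discontinuation if signs or symptoms come back on rechallenge. Section 6.4.1 requires permanent discontinuation for a combined enzyme and bilirubin or INR pattern when there is no confounding factor, and 6.4.3 bars rechallenge for those subjects.

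**CRS rules (Protocol 6.6, Table 5, 6.2.1.4).** Section 6.6 lists fever, nausea, vomiting, transaminitis and hyperbilirubinemia among CRS manifestations. The Table 5 grade 1 row reads "Symptoms are not life threatening and require symptomatic treatment only, eg, fever, nausea, fatigue, headache, myalgias, malaise", and its interruption column is marked N/A. The grade 2 row includes "Grade 2 organ toxicity or grade 3 transaminitis per CTCAE criteria" and names worsening or persistent hypotension as the interruption trigger. Section 6.2.1.4 makes interruption mandatory for every grade 2 or 3 CRS. On re-start, 6.6 says: "After grade 2 or 3 CRS, the next infusion may be administered if all of the following criteria are met". The criteria are medical monitor consultation, a 72-hour interruption if CRS occurred during the infusion, and resolution to grade 1 or lower. Treatment then resumes one dose level down.

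**Scope of 6.4.2.** One of its two covered groups is subjects with no underlying liver disease and "eligibility criteria requiring normal transaminases and TBL at baseline"; the other is subjects with underlying liver disease and abnormal baseline transaminases. Inclusion criterion 106 admits AST and ALT up to 3.0 x ULN and bilirubin up to 1.5 x ULN.

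**The concern.** By the protocol's own list, fever with a rise in liver enzymes can be CRS. The same picture can also trigger the hepatotoxicity rules. Section 6.4 does not mention CRS. Section 6.6 does not mention 6.4, and its general re-start pointer goes to 6.2.1.4. An investigator therefore has two sets of conditions for re-dosing the same subject and no statement of which governs.

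At stake is whether a subject is re-dosed or discontinued. That feeds the exposure summaries (SAP 9.6.8), the tables of adverse events leading to withdrawal (SAP 9.6.2) and the administration data that the DLRT reviews. CRS is the identified risk for this drug, so the overlap concerns an expected event. If sites or medical monitors resolve it differently, those summaries will partly reflect which section was read.

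**Working it through.** No statistical input or published figure bears on this point, so the check sets the passages side by side.

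**1. Re-start and recurrence.**

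| | CRS rules (6.6, 6.2.1.4), after grade 2-3 CRS | Hepatic rules (6.4.2, 6.4.3) |
|---|---|---|
| Cause | No condition | Alternative cause must be found |
| Recovery | CRS grade 1 or lower | Values normal or at baseline |
| Minimum hold | 72 hours if CRS arose during infusion | None stated |
| Sponsor contact | Medical monitor consulted | Medical monitor discussion |
| Dose at re-start | One level lower | None stated |
| Recurrence | Step-up allowed if no grade 3 or higher CRS at the lower dose; permanent stop for, among others, two separate grade 3 events | Permanent stop if signs or symptoms recur |

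Take a subject whose enzymes met a 6.4.2 trigger within grade 2 or 3 CRS, who has met all the CRS re-start criteria, and in whom no other cause has been found. Two questions remain: does CRS count as an alternative cause, and are the values normal or at baseline? That gives 2 x 2 = 4 combinations. The CRS rule permits re-start in all 4. Section 6.4.2 permits it to be considered in 1 (yes to both). The rules part in 4 - 1 = 3. This counts logical cases; it is not a frequency. Even where they agree on re-start, they differ on recurrence: a later grade 1 or 2 CRS with liver signs is a permanent stop under 6.4.3 but not automatically so under 6.6 and 6.2.1.4.

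**2. Permanent discontinuation under 6.4.1.** The pattern is ALT or AST at least 3 x ULN, with total bilirubin at least 2 x ULN or INR at least 1.5, ALP no more than 2 x ULN, and no confounder. Section 6.6 lists both transaminitis and hyperbilirubinemia as CRS signs. If CRS is a confounder, 6.4.1 is not met and re-start remains possible. If it is not, the subject stops for good. The list of causes in 6.4.1 is open-ended; it names hypotension but not CRS.

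**3. Grade 1 overlap in withholding.** This depends on the CTCAE cut-off T at which transaminitis becomes grade 3, which the documents do not give. As an assumption over a range:

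- T at or below 3 x ULN: no grade 1 overlap.
- T = 5 x ULN: overlap for values above 3 and up to 5 x ULN.
- T = 8 x ULN: overlap for values above 3 and up to 8 x ULN.

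It also assumes that lower-grade transaminitis is not itself grade 2 organ toxicity in the Table 5 sense. Within the overlap, Table 5 gives no interruption instruction and 6.4.2 recommends withholding, provided the symptoms are judged consistent with hepatitis. Steps 1 and 2 do not depend on T.

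**4. Grade 2 interruption.** Table 5 ties interruption to hypotension; 6.2.1.4 requires it for every grade 2 event. A grade 2 event defined by grade 3 transaminitis without hypotension gets different instructions from the two places.

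**5. Scope of 6.4.2.** A subject with no liver disease and baseline AST or ALT above ULN but within 3.0 x ULN is eligible under criterion 106. That subject is not in the first group, which presumes normal baseline values, nor in the second, which requires liver disease. Read strictly, the first group is empty here, because this protocol has no such eligibility criterion.

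**The case against.** The strongest reply is that the two rule sets can usually be followed together. A reader might infer that a subject with grade 1 CRS is required both to continue and to be withheld. The text does not support that: N/A in Table 5 is the absence of a CRS-specific interruption instruction, not an order to dose, and 6.4.2 only recommends. Withholding satisfies both.

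A reader might also take Table 5 alone and conclude that ALT at 9 x ULN within grade 2 CRS is interrupted only for hypotension. Section 6.2.1.4 requires interruption of every grade 2 or 3 CRS, so the CRS and hepatic rules both stop dosing there and differ on re-start.

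A third tempting step is to put a figure on lost DLT-evaluability in Schedule B from missed target doses. Neither rule fixes the number of doses missed, the mandatory CRS interruption could cost the same doses, and 6.2.1.4 asks for the planned infusions, or the 70% minimum, to be made up where possible. No such figure separates the two rules.

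It is also fair that both routes pass through the medical monitor, which limits divergence between sites, that the 6.4.1 list does not exclude CRS, and that hepatitis-like symptoms need investigator judgement. These points narrow the problem. They do not supply a precedence rule or make the re-start and recurrence conditions the same.

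**Conclusion.** The point holds as an unreconciled overlap of safety rules. Its firmest part is re-start and recurrence after grade 2 or 3 CRS: the same subject can meet the CRS conditions and fail those of 6.4.2, and this rests on no outside cut-off. Whether CRS counts as an alternative or confounding cause decides the outcome under 6.4.2, and under 6.4.1 can decide between permanent discontinuation and possible re-start; the documents are silent. At CRS grade 1 there is an unresolved overlap in withholding, whose width depends on the assumed CTCAE cut-off and on how organ toxicity is read. The 6.4.2 scope sentence and criterion 106 do not fit together, which is a separate drafting defect. The effect on exposure and discontinuation counts is real in principle but cannot be sized from the documents. No sample size, interval or model specification changes.

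**What to change.** - Reconcile 6.4.1-6.4.3 with Table 5, 6.6 and 6.2.1.4, including the Table 5 grade 2 interruption instruction against the mandatory interruption in 6.2.1.4.
- State in both the hepatic and the CRS sections which one governs withholding, re-start and recurrence when liver tests rise within CRS.
- State whether CRS counts as an alternative cause under 6.4.2 and as a confounding factor under 6.4.1.
- Rewrite the 6.4.2 scope sentence so that it covers the subjects whom criterion 106 admits.

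Which rule prevails is for the sponsor's clinical and hepatic safety reviewers. The cost is protocol wording in an amendment; no assessments are added and no analysis is altered.

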6.4.3 Criteria for Rechallenge of AMG 673 After Potential Hepatotoxicity

If signs or symptoms recur with rechallenge, then the investigational product should be permanently discontinued. Subjects who clearly meet the criteria for permanent discontinuation (as described in [Section 6.4.1](#)) should never be rechallenged.

6.5 Concomitant Therapy

Throughout the study, Investigators may prescribe any concomitant medications or treatments deemed necessary to provide adequate supportive care except for those listed in [Section 6.9](#).

Concomitant therapies are to be collected from informed consent, through the EOS. For all concomitant therapies collect therapy name, indication, dose, unit, frequency, route, start date, and stop date.

6.6 Specific Recommendations for Cytokine Release Syndrome, Tumor Lysis Syndrome and Infection Prophylaxis

Cytokine Release Syndrome

CRS is clinically defined and may have various manifestations. There are no established diagnostic criteria. Signs and symptoms of CRS may include:

- Constitutional – fever, rigors, fatigue, malaise
- Neurologic – headache, mental status changes, dysphasia, tremors, dysmetria, gait abnormalities, seizure
- Respiratory – dyspnea, tachypnea, hypoxemia
- Cardiovascular – tachycardia, hypotension
- Gastrointestinal – nausea, vomiting, transaminitis, hyperbilirubinemia
- Hematology – bleeding, hypofibrinogenemia, elevated D-dimer
- Skin – rash

Subjects may experience CRS, identified as a safety risk factor for AMG 673 treatment, during the first few days following the initial infusion of AMG 673 and after a dose step. CRS may be life-threatening or fatal. Infusion reactions may be clinically indistinguishable from manifestations of CRS. Throughout the infusion with AMG 673 and at least 4 hours after the end of infusion, monitor subjects intensively for clinical signs (eg, fever, hypotension, tachycardia, dyspnea, tremors) and laboratory changes (eg, transaminase increase) which may be related to CRS.

Grading and management of CRS should be performed according to the guidelines provided in [Table 5](#) [based on the adopted grading system referenced in [Lee et al, 2014](#)].

Approved

Table 5. Grading and Management of Cytokine Release Syndrome

CRS Grade	Description of Severity ^a	Minimum Expected Intervention	Instructions for Interruption of AMG 673
1	Symptoms are not life threatening and require symptomatic treatment only, eg, fever, nausea, fatigue, headache, myalgias, malaise	
 Administer symptomatic treatment (eg, paracetamol/ acetaminophen for fever, fluids for hypotension). Consider use of tocilizumab 8 mg/kg iv. Up to 3 additional doses can be given 8 hours apart, if needed. Monitor for CRS symptoms including vital signs and pulse oximetry at least Q2 hours for 12 hours or until resolution, whichever is earlier. 	N/A
2	Symptoms require and respond to moderate intervention 
 Oxygen requirement < 40%, OR Hypotension responsive to fluids or low dose of 1 vasopressor, OR Grade 2 organ toxicity or grade 3 transaminitis per CTCAE criteria 	Administer: 
 Symptomatic treatment (eg, paracetamol/ acetaminophen for fever, vasopressors for hypotension) Supplemental oxygen when oxygen saturation is < 90% on room air Intravenous fluids or low dose vasopressor for hypotension when systolic blood pressure is < 100 mmHg. Persistent tachycardia (eg > 120 bpm) may also indicate the need for intervention for hypotension. Consider use of tocilizumab 8 mg/kg IV . Dose may be repeated every 8 hours for up to 3 additional doses. Monitor for CRS symptoms including vital signs and pulse oximetry at least Q2 hours for 12 hours or until resolution to CRS grade ≤ 1, whichever is earlier. For subjects with extensive co-morbidities or poor performance status, manage per grade 3 CRS guidance below.	Institute medical management. If hypotension worsens or persists 2 hours after adequate medical management, interrupt AMG 673 until CRS is Grade ≤ 1. Refer to re-start criteria below. If symptoms progress to grade 3 criteria, see row below. Permanently discontinue AMG 673 if there is no improvement to CRS ≤ grade 1 within 7 days.

Approved

Footnotes defined on next page of the table

Table 5. Grading and Management of Cytokine Release Syndrome

CRS Grade	Description of Severity^a	Minimum Expected Intervention	Instructions for Interruption of AMG 673
3	Symptoms require and respond to aggressive intervention 
 • Oxygen requirement $\geq 40\%$, OR • Hypotension requiring high dose^b or multiple vasopressors, OR • Grade 3 organ toxicity or grade 4 transaminitis per CTCAE criteria 	Admit to intensive care unit for close clinical and vital sign monitoring per institutional guidelines. Administer dexamethasone (or equivalent) IV at a dose maximum of 3 doses of 8 mg (24 mg/day). The dose should then be reduced step-wise. Administer tocilizumab as an additional therapy in this setting at a dose of 8 mg/kg. Dose may be repeated every 8 hours for up to 3 additional doses.	Immediately interrupt AMG 673 until event resolves to CRS grade ≤ 1 . Permanently discontinue AMG 673 if there is no improvement to CRS \leq grade 2 within 5 days or CRS \leq grade 1 within 7 days. Permanently discontinue AMG 673 if CRS grade 3 occurs at the initial run in dose (ie, at MTD1).
4	Life-threatening symptoms 
 • Requirement for ventilator support OR • Grade 4 organ toxicity (excluding transaminitis) per CTCAE criteria 	Admit to intensive care unit for close clinical and vital sign monitoring per institutional guidelines. Administer dexamethasone (or equivalent) IV at a dose maximum of 3 doses of 8 mg (24 mg/day). Further corticosteroid use should be discussed with the Amgen medical monitor. Additionally, tocilizumab should be administered at a dose of 8 mg/kg. Dose may be repeated every 8 hours for up to 3 additional doses.	Immediately stop the infusion and permanently discontinue AMG 673 therapy.

Approved

Page 2 of 2

CRS, Cytokine Release Syndrome; CTCAE, Common Terminology Criteria for Adverse Events;

IV, Intravenous; MTD = maximum tolerated dose

^a Revised grading system for CRS (Lee et al, 2014)

^b High dose vasopressors (all doses are required for ≥ 3 hours): Norepinephrine monotherapy ≥ 20 $\mu\text{g}/\text{min}$; Dopamine monotherapy ≥ 10 $\mu\text{g}/\text{kg}/\text{min}$, Phenylephrine monotherapy ≥ 200 $\mu\text{g}/\text{min}$, Epinephrine monotherapy ≥ 10 $\mu\text{g}/\text{min}$; If on vasopressin, vasopressin + norepinephrine equivalent of ≥ 10 $\mu\text{g}/\text{min}$; If on combination vasopressors (not vasopressin), norepinephrine equivalent of ≥ 20 $\mu\text{g}/\text{min}$

Re-start of treatment after CRS:

After grade 2 or 3 CRS, the next infusion may be administered if all of the following criteria are met:

- The Amgen medical monitor must be consulted prior to re-starting treatment
- If CRS occurred during AMG 673 infusion, infusion has been interrupted for at least 72 hours
- The event has resolved to grade ≤ 1 prior to re-starting treatment

AMG 673 therapy should be restarted 1 dose level below the dose at which the event occurred. If this lower dose level is well tolerated (ie, absence of grade ≥ 3 CRS), then a dose step up to the subject's target dose level can occur. An intermediate dose may be administered after consultation with the Amgen medical monitor prior to stepping up to the target dose.

Please also refer to the general guidance for re-start of treatment after adverse events in [Section 6.2.1.4](#)

For Grade 3 and 4 CRS, please see [Section 2](#) for DLT considerations.

Tumor Lysis Syndrome

Subjects with AML and WBC $<10,000/\text{mcl}$ or $10 \text{ cells} \times 10^9/\text{L}$ are considered to be at low risk for tumor lysis syndrome. WBC $>10,000/\text{mcl}$ and $<50,000/\text{mcl}$ are considered to be at intermediate risk, and subjects with WBC $>50,000/\text{mcl}$ are considered at high risk. This protocol requires that subjects have a maximum WBC count of $15,000/\text{mcl}$ or $15 \text{ cells} \times 10^9/\text{L}$.

Additional high-risk features include baseline uric acid $>450 \text{ mcg/L}$ (7.5 mg/dl), serum creatinine $> 1.4 \text{ mg/dL}$, and lactate dehydrogenase (LDH) greater than the ULN.

Patients with intermediate risk WBC count and elevated baseline uric acid ($> 450 \text{ mcg/L}$), serum creatinine $>1.4 \text{ mg/dl}$, or LDH greater than ULN will be recommended to receive allopurinol prophylaxis. Typical dosing is 600-800 mg/day administered BID or QID and should begin 3 days before the first dose of study drug. Patients should be well hydrated and supplemented with intravenous fluid as clinically indicated.

For grade 3 and 4 tumor lysis syndrome, please see [Section 6.2.1.3](#) for DLT considerations.

Infection Prophylaxis

Subjects who may experience neutropenia for 7 days or longer are at a high risk for infectious complications. As appropriate, these subjects should be administered prophylactic antibacterial (eg, fluoroquinolones), antifungal and antiviral medications. These subjects should be monitored for early signs of breakthrough infections after the initiation of antibacterial therapy to prompt additional evaluation and possible therapy modification.

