7.3.10 Events

Adverse event and serious adverse event as well as disease-related event assessments will be made throughout the study and will be evaluated and recorded in the source documents and on the eCRF as specified in [Sections 9.2](#) and [9.1.1](#), respectively. The severity of all events will be graded according to CTCAE, version 4.0 ([Appendix A](#)) unless specified otherwise. **Exception:** CRS will be graded according to the adopted grading system referenced in ([Lee et al, 2014](#), see [Table 5](#)).

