9.2.2 Adverse Events

9.2.2.1 Reporting Procedures for Adverse Events That do not Meet Serious Criteria

The investigator is responsible for ensuring that all adverse events observed by the investigator or reported by the subject that occur after consent through the end of study are reported using the Event CRF.

The investigator must assign the following adverse event attributes:

- Adverse event diagnosis or syndrome(s), if known (if not known, signs or symptoms),
- Dates of onset and resolution (if resolved),
- Severity [and/or toxicity per protocol],
- Assessment of relatedness to investigational products, medical devices (syringe, infusion pump), or study procedure / activity
- Action taken.

The adverse event grading scale used will be the CTCAE, version 4.0. The grading scale used in this study is described in [Appendix A](#). **Exception:** CRS will be graded according to the guidelines provided in [Table 5](#) [based on the adopted grading system referenced in [Lee et al 2014](#)].

The investigator must assess whether the adverse event is possibly related to the investigational products, medical devices and/or study procedure / activity. This relationship is indicated by a “yes” or “no” response to the question: Is there a reasonable possibility that the event may have been caused by the investigational product, medical device, and/or study procedure / activity?

The investigator is responsible for reviewing laboratory test results and determining whether an abnormal value in an individual study subject represents a clinically significant change from the subject's baseline values. In general, abnormal laboratory findings without clinical significance (based on the Investigator's judgment) are not to be recorded as adverse events. However, laboratory value changes that require treatment or adjustment in current therapy are considered adverse events. Where applicable, clinical sequelae (not the laboratory abnormality) are to be recorded as the adverse event.

The investigator is expected to follow reported adverse events until stabilization or reversibility.

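### Table 5 lists fluids for hypotension under grade 1 CRS care, although its severity column makes fluid-responsive hypotension grade 2

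*Protocol*

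**What the plan says.** Table 5 in protocol Section 6.6 has a severity column, a minimum-intervention column and an interruption column. Four cells matter here.

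- Grade 1, severity: "Symptoms are not life threatening and require symptomatic treatment only, eg, fever, nausea, fatigue, headache, myalgias, malaise". Hypotension is not among the examples.
- Grade 1, intervention: symptomatic treatment, with the examples "acetaminophen for fever, fluids for hypotension".
- Grade 2, severity: three criteria joined by OR, one of which is "Hypotension responsive to fluids or low dose of 1 vasopressor".
- Grade 2, intervention: "Intravenous fluids or low dose vasopressor for hypotension when systolic blood pressure is" below 100 mmHg, among other measures.

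Several places say how the grade is set. Section 6.6 says "Grading and management of CRS should be performed according to the guidelines provided in" Table 5. Section 7.3.10 says "CRS will be graded according to the adopted grading system referenced in" the cited publication, and points to Table 5. Section 9.2.2.1 says "CRS will be graded according to the guidelines provided in" Table 5, and SAP Section 9.6.2 also uses that table. Footnote a of Table 5, "Revised grading system for CRS", is attached to the heading of the severity column only.

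**The concern.** The same clinical event, hypotension that is given fluids and responds, appears as an example of care in the grade 1 row and as a defining criterion in the grade 2 row. The examples of symptomatic treatment also move from fluids in the grade 1 row to vasopressors in the grade 2 row. A site working along the rows could reasonably infer that fluids mean grade 1 and vasopressors mean grade 2.

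The boundary between the two grades matters. The re-start rules after CRS begin at grade 2, and grade 1 is the level to which an event must fall to count as resolved. Section 3.1 uses grade 2 as the bar to intra-subject dose escalation. Grade is part of the primary endpoint (Section 10.1.1), and CRS / infusion reactions is the only identified risk in Table 1.

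**Working it through.** No arithmetic applies. The check compares the cells and then traces where the grade is used.

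**Step 1. Does the severity column leave any fluid-responsive hypotension for grade 1?** The grade 1 symptom list is only illustrative, so it does not by itself exclude hypotension. The grade 2 criterion does. It is sufficient alone, it has no blood pressure floor, and it covers every hypotension that responds to fluids. Hypotension that does not respond to fluids needs a vasopressor, which is grade 2 at low dose and grade 3 at high dose or with several agents. Hypotension needing fluids is therefore at least grade 2.

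**Step 2. Does the 100 mmHg figure separate the grades?** No. It stands in the grade 2 intervention cell and says when to treat. It is not in either severity cell.

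**Step 3. Which column sets the grade?** Footnote a ties the grading system to the severity column, and Section 7.3.10 ties grading to that system. The answer is grade 2.

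**Step 4. What changes if 1 is recorded instead of 2?**

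| Rule | After grade 1 | After grade 2 | Does the difference hold? |
|---|---|---|---|
| Medical monitor consulted before re-start (Sections 6.2.1.4, 6.6) | Not listed | Required | Yes |
| Re-start one dose level lower (Section 6.6) | Not listed | Stated | Yes |
| Intra-subject escalation | Not barred | Barred for treatment-related events by Section 3.1 (grade 2 or above) | Depends on the text followed: the synopsis and SAP Section 3.1 say grade 3 or above |
| Grade in the primary endpoint | 1 | 2 | Yes |
| Infusion interrupted at least 72 hours (Section 6.6) | Not listed | Only if CRS occurred during the infusion | Conditional |
| Treatment interruption | Not applicable | Section 6.2.1.4: mandatory. Table 5: if hypotension worsens or persists 2 hours after adequate management | Uncertain |
| DLT or permanent discontinuation (Sections 6.2.1.3, 6.2.1.4) | No grade 1 rule | Only if not resolved to grade 1 or less within 7 days | Unlikely to matter for fluid-responsive hypotension |

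Section 6.6 lists three re-start criteria after grade 2 or 3 CRS. One always applies (the medical monitor), one depends on when CRS occurred, and one is met once the event has resolved to grade 1 or less. Counting them does not measure harm.

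**The case against.** The strongest reply is that the documents already settle the grade. The severity column carries the grading system, a careful site would assign grade 2, and what remains is one example in a management column that uses the term symptomatic treatment loosely; the grade 2 cell places vasopressors under the same term. This stands as a limit on how often misgrading would happen. It does not remove the conflict, because Section 6.6 sends sites to the whole table for both grading and management.

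A second reply is that the authors may have meant mild dips managed with supportive fluids to be grade 1 and left out a threshold. The severity wording does not say so. If that was the intention, the table still needs correcting.

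A third reply concerns harm, and most of it stands. A reader might infer that under-grading means dosing continues when it should stop. The documents do not support that firmly. Section 6.2.1.4 says grade 2 CRS must lead to interruption, but it refers to Section 6.6 for details, and Table 5 there interrupts only for hypotension that worsens or persists. Hypotension that responds promptly to fluids would usually not meet that condition. Table 5 also mentions the re-start criteria directly after its interruption instruction, which could suggest that they apply only after an interruption. The re-start text itself, however, is worded for any grade 2 or 3 CRS.

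A reader might also infer that DLT counts, and so the dose-escalation model, would be distorted. That would need CRS still unresolved at 7 days, which is unlikely for this event. Grades 1 and 2 share the 2-hourly monitoring and the option of tocilizumab, and the dose level review team sees all available data (Section 10.3.2).

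**Conclusion.** The inconsistency is real and lies within one current table. Grade 2 is the right grade for fluid-responsive hypotension, and the grade 1 example is misplaced. The error, where it occurs, is one grade per event. Three consequences follow from the text: no medical monitor consultation before re-start, no re-start one dose level lower, and a wrong CRS grade in the primary endpoint. Possible eligibility for intra-subject escalation is a fourth, if a site follows Section 3.1 rather than the synopsis. A related weakness is that a subject still receiving fluids for hypotension could be called grade 1 and so counted as resolved. Loss of an interruption is uncertain, and the 72-hour condition applies only to CRS during the infusion.

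The conclusion assumes that some sites read across rows rather than grading from the severity column. The documents give neither the frequency of fluid-treated hypotension nor that of misgrading, so the effect on the trial cannot be sized. Severity: minor.

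**What to change.** Delete the hypotension example from the grade 1 intervention cell, leaving only the fever example. Add one line under Table 5: *CRS is graded from the Description of Severity column; hypotension needing fluids is at least grade 2.* This restates the existing severity column and makes no new clinical choice.

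The cost is one phrase deleted, one line added and a short note to sites. The small downside is that some events that sites may now call grade 1 will follow the grade 2 re-start rules. As an option, the sponsor can check existing grade 1 CRS records for fluid-treated hypotension.
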